8 CONCOMITANT MEDICATIONS AND NON-DRUG THERAPIES

Refer to the corresponding section in Protocol 103A-301.

9 ASSESSMENT OF EFFICACY

Subjects will be assessed for efficacy as described in Section 9.3 of Protocol 103A-301.

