9.3 Part B Clinical Efficacy Parameters

Survival time is computed based on the date of death if the subject is known dead or the date last known to be alive (censored). Zero time for a subject is the date of randomization.

Recurrence-free survival time (RFS) is computed from the earliest of the date of recurrence or death or, if without recurrence or death, the date last assessed for recurrence without a diagnosis of recurrence (censored). The date of recurrence is specified as the first date a recurrence is suspected, which is later confirmed by biopsy. In the rare cases where biopsies are not clinically appropriate (e.g., brain metastases), the recurrence date will be set by the treating clinician's medical judgment. Zero time for a subject is the date of randomization.

Recurrence will be monitored through tumor imaging (as specified in Section 9.3.1) every 6 months until recurrence, death, subject withdrawal, early termination or completion of the study.

LDH is also monitored every 3 months for early indication of possible recurrence. LDH elevations of 1.5 X ULN (or greater) will be followed up with radiological scans, provided there are no other obvious medical reasons for the elevated LDH.

Recurrence is defined as the occurrence of the following events:

- Loco-regional relapse
- Distant metastasis
- A new melanoma that is likely unrelated to the original primary lesion

Investigators are required to obtain biopsies of recurrent tumors to provide pathologic evidence of recurrence unless the recurrence is in the brain. In the case of multiple lesions during an imaging examination, biopsy of at least one lesion should be obtained.

As the determination of recurrence will primarily rely on biopsies, there will be no central reading of CT scans to confirm recurrence.

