2 OBJECTIVES

- To evaluate the safety of seviprotimut-L in subjects who received placebo in Part A of Protocol 103A-301.
- To assess the efficacy (defined as recurrence-free survival [RFS] and overall survival [OS]) of treatment with seviprotimut-L in subjects who received placebo in Part A of Protocol 103A-301.

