4 PARTICIPANT SELECTION

To be eligible for this OLE study, all of the following conditions must be met:

1. Subject was randomized into the placebo arm of Part A of Protocol 103A-301.

2. Subject is eligible to receive study drug at the time of IRB approval for this OLE study, i.e., disease has not recurred and the subject has been actively participating in the Part A portion of the trial.
3. Subject is an appropriate candidate for treatment with seviprotimut-L, in the opinion of the site investigator.
4. Subject must have known BRAF V600E mutation tumor status or have tumor tissue (fresh or archived sample) available for testing of BRAF V600E mutation status (note: as long as it is confirmed that tumor tissue is available for testing, the subject may be considered eligible for the study; testing of BRAF mutation status on that tissue may be conducted at a later time during the study). A new sample is not needed if the sample has already been tested or reconciled prior during the Part A portion of the trial.
5. Subject is able to give written informed consent and/or comply with the study procedures.

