11 STATISTICAL CONSIDERATIONS

Safety data will be tabulated and descriptive statistics will be used to summarize all other results.

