5.0 STATISTICAL CONSIDERATIONS

5.1 Part A

The size of Part A (33 patients per arm) was computed based on having no greater than a one-sided 20% likelihood of a false positive conclusion for the immune response statistical criterion. See the subsequent section [6.8.1 “Part A Immunological Statistical Success”](#) for the statistical operating characteristics of the Part A statistical analysis.

Recruitment will continue in Part A until the analysis of Week 10 data has been completed on the first 99 randomized subjects. This will result in an “over enrollment” for Part A to avoid a discontinuation of recruitment and ensure a complete data set for Part A evaluation.

Patients assigned to the Placebo arm during Part A accrual will be offered the option of receiving 40 µg seviprotimut-L selected from Part A under an Open-Label Extension protocol. Patients assigned to the Part A active arms will remain on the dose assigned and be followed until the end of the study. All Part A patients will be separately tabulated and used in the assessment of safety. They may also be used in exploratory efficacy analyses, but will not be part of the primary or secondary Part B evaluations.

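### The open-label extension takes its RFS and OS time origin from Part A randomisation to placebo, so event-free placebo time required for entry is counted in the vaccine's descriptive efficacy results

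*Protocol*

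**What the plan says.** Appendix C Section 2 gives the extension an efficacy objective: "To assess the efficacy (defined as recurrence-free survival [RFS] and overall survival [OS]) of treatment with seviprotimut-L in subjects who received placebo" in Part A. SAP 3.2 and 3.5 repeat it, with RFS and OS as endpoints.

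The only efficacy rule is Appendix C Section 9: "Subjects will be assessed for efficacy as described in Section 9.3 of Protocol 103A-301". Main protocol Section 9.3 says, once for survival and once for RFS: "Zero time for a subject is the date of randomization".

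Appendix C Section 4 sets the entry conditions. One is "Subject was randomized into the placebo arm of Part A of Protocol 103A-301". Another is that "disease has not recurred and the subject has been actively participating in the Part A portion of the trial".

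Appendix C Section 11 limits the analysis: "Safety data will be tabulated and descriptive statistics will be used to summarize all other results". Appendix C Section 3.4 caps enrolment at 53. SAP 2.1 keeps extension outcomes out of the evaluation of Parts B1 and B2.

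**The concern.** The extension randomises nobody, so the only randomisation date its subjects have is the Part A one, when they were assigned to placebo. Vaccine starts later, at extension Week 0. A subject who recurred or died in between cannot be in the extension. Every RFS and OS time measured from randomisation therefore opens with a stretch in which no event was possible and no vaccine was given. This is immortal-time bias, and it favours the vaccine.

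At stake is the answer to the extension's own efficacy objective. A Kaplan-Meier curve or median built this way is too favourable even without a formal test. It would mislead further if set beside curves from Part A, Part B or published trials, which start at randomisation without such selection.

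**Working it through.** **Does any other text reset the origin?**

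- SAP 6.0 defines extension baseline as the last value before extension dosing. That governs change-from-baseline summaries, not a time-to-event origin.
- SAP 6.9.1 and 6.9.2 define the OS and RFS times. They are written for Parts B1 and B2 and subtract the randomisation date. Addendum #1 adds that this date comes from the IVRS.
- Appendix C names a Week 0 for visits but does not tie RFS or OS to it.

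Nothing resets it.

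**How large could the effect be?** The plan states no event count, power or expected RFS for the extension, so there is no figure to reproduce. The following is an illustration.

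Inputs from the table in SAP 5.2.1 (control arm, empirical proportions):

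| Stage | Proportion | Median RFS (y) | Stated rate (/y) | ln 2 / median |
|---|---|---|---|---|
| II | 0.309 | 4.5 | 0.154 | 0.1540 |
| IIIA | 0.304 | 3.5 | 0.198 | 0.1980 |
| IIIB/C | 0.387 | 1.7 | 0.409 | 0.4077 |

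The stated rates agree with the medians to within rounding.

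Assume that the vaccine has no effect. Placebo RFS is then

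S(t) = 0.309·exp(−0.154t) + 0.304·exp(−0.198t) + 0.387·exp(−0.409t).

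At 2 years, S(2) = 0.227 + 0.205 + 0.171 = 0.602 before rounding of the terms. This is the true 2-year RFS.

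Let c be the time from Part A randomisation to the first extension dose. The documents do not give it, so I take 0.25, 0.5 and 1 year as assumptions. Given freedom from events at c:

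- timed from Part A randomisation, 2-year RFS is S(2)/S(c);
- timed from the first extension dose, 2-year RFS is S(c + 2)/S(c).

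| c (y) | S(c) | 2-year RFS from randomisation | 2-year RFS from first extension dose |
|---|---|---|---|
| 0.25 | 0.936 | 0.602/0.936 = 64.4% | 0.567/0.936 = 60.6% |
| 0.5 | 0.877 | 0.602/0.877 = 68.7% | 0.535/0.877 = 61.0% |
| 1 | 0.771 | 0.602/0.771 = 78.1% | 0.476/0.771 = 61.7% |

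(Percentages use unrounded values.)

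The medians behave the same way. Unselected placebo has a median of 2.79 years. Timed from randomisation, extension entrants show 3.07, 3.36 and 3.93 years; timed from first dose, 2.82, 2.86 and 2.93 years. The difference in each row is exactly c.

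The small excess that remains after timing from first dose arises because higher-risk stages recur earlier, so those still eligible are a somewhat better-risk group.

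OS cannot be quantified, because the documents give no control-arm death rates. The direction is the same, since entrants must be alive.

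**The case against.** Four points can be made against this.

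**The cross-reference may not be meant to carry the time origin.** Section 9.3 also holds the imaging, LDH and biopsy rules, it sits under a Part B heading, and its zero-time sentence presupposes a randomisation that the extension lacks. This is a fair reading. On it, however, the extension's RFS and OS have no time origin at all, which needs the same sentence to repair.

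**The harm is bounded.** The summaries are descriptive and no comparator is planned. Protocol 7.2.3 admits only Part B subjects' efficacy data to the clinical efficacy analysis. All of this stands. It limits the consequences but does not correct the curve that answers a stated objective.

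**The gap may be short.** Under Protocol 5.3.4, Part A recruitment continued until the Week 10 analysis of the first 99 subjects was complete. Late entrants need not have reached Week 10 when placebo subjects were unblinded, so no minimum gap can be claimed for everyone. The size of the bias depends on the gap; its direction does not.

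**Two stronger inferences go too far.** A reader might infer that a 1-year gap alone produces an artefact beyond the hypothesised RFS hazard ratio of 0.625. That depends on choices the documents do not make. With the inputs above, the crude event-rate ratio against unselected placebo is 0.59 over 3 years from randomisation, 0.66 over 4 years and 0.70 over 5 years. Against the same subjects timed from first dose over 3 years of extension follow-up, it is 0.68. A crude rate ratio is also not the hazard ratio used to plan the trial.

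A reader might also infer that Part A comparisons of vaccine with placebo after unblinding are compromised. SAP 5.1 says of Part A patients only that "They may also be used in exploratory efficacy analyses". It specifies no such comparison, and placebo subjects who enter the extension keep 6-monthly tumour assessments there.

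**Conclusion.** The point holds. Read together, Appendix C Section 9, Protocol 9.3 and the entry conditions in Appendix C Section 4 put event-free placebo time into the RFS and OS reported for the vaccine, and no other text removes it.

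In the illustration, a 2-year RFS of 60% is overstated by about 4, 8 and 18 percentage points for gaps of 0.25, 0.5 and 1 year. Timing from first dose leaves an excess of no more than about 1.5 points. These figures assume exponential RFS within stage, the SAP's control rates and empirical stage mix, no vaccine effect, and a gap common to all subjects; the true gaps are not stated.

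The reach is small: up to 53 subjects, descriptive output only, and no effect on the primary analyses or type I error of Parts B1 and B2. The documents do not support a claim that the artefact exceeds the trial's hypothesised effect, or a finding against an unspecified Part A comparison.

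**What to change.** In Appendix C Section 9, with a matching line in SAP 6.9, state that zero time for extension RFS and OS is the date of the first seviprotimut-L dose under 103A-301OL. If randomisation is to be kept as the origin, use delayed entry (left truncation) at that date instead.

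Also report the distribution of time from Part A randomisation to extension entry, and state that extension results are not to be set beside curves timed from randomisation.

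The cost is a few lines of text. The dates needed are already collected, and no procedure changes. The drawback for the sponsor is that the reported extension RFS and OS will look less favourable.

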10 ASSESSMENT OF SAFETY

Refer to the corresponding section in Protocol 103A-301.

11 STATISTICAL CONSIDERATIONS

Safety data will be tabulated and descriptive statistics will be used to summarize all other results.

12 STUDY CONDUCT CONSIDERATIONS

Refer to the corresponding section in Protocol 103A-301.

13 REFERENCES

Refer to the corresponding section in Protocol 103A-301.

SCHEDULE OF ACTIVITIES FOR PROTOCOL 103A-301OL

Procedure	Pre-Dosing	Dosing Period															Pre-Recurrence		Post-Recurrence	End of Study ¹
		First Visit (W0)	W 2	W 4	W 6	W 8	M 3	M 4	M 5	M 6	M 9	M 12	M 15	M 18	M 21	M 24	Q 3 Mos	Q 6 Mos	Q 6 Mos	
Baseline Documentation																				
Informed Consent	X																			
Physical Exam		X ²					X			X	X	X	X	X	X	X	X	X	X	
BRAF mutation status ³	X																			
Laboratory Studies																				
LDH		X					X			X	X	X	X	X	X	X	X	X	X ⁴	
CBC and serum chemistry		X	X	X	X	X	X			X		X	X	X	X	X	X	X	X	
Urinalysis		X	X	X	X	X	X			X		X	X	X	X	X	X	X	X	
Pregnancy test																			X	
ECG																			X	
ANA/ESR	X ⁵									X		X		X		X		X		
Tumor Assessments																				
Recurrence Assessment	X ⁶									X		X		X		X		X		
Dosing																				
Seviprofutim-L		X	X	X	X	X	X	X	X	X	X	X	X	X	X	X	X			
Other Clinical Assessments																				
Survival Follow-up Contact																			X	
Autoimmune Phenomena ⁷	X ⁸									X		X		X		X				
Adverse Events		X	X	X	X	X	X	X	X	X	X	X	X	X	X	X	X	X ⁹		
Concomitant Medications		X	X	X	X	X	X	X	X	X	X	X	X	X	X	X	X	X ¹⁰	X	

Note: Visit windows are \pm 3 days for Weeks 2, 4, 6, and 8; and \pm 7 days for subsequent visits.

¹ At time of recurrence or study completion for subjects without recurrence

² If not performed within 30 days prior to planned first dose under Protocol 103A-301OL

³ BRAF tumor mutation V600E status must be either known at Screening or a tumor tissue (fresh or archived sample) must be available for testing during the Study.

⁴ For subjects who have not had recurrent disease

⁵ If not performed within 30 days prior to planned first dose under Protocol 103A-301OL

⁶ If not performed within 30 days prior to planned first dose under Protocol 103A-301OL

⁷ Include eye exam (by an ophthalmologist) and skin exam for vitiligo and rashes thereafter.

⁸ If not performed within 30 days prior to planned first dose under Protocol 103A-301OL

⁹ Adverse events collected through 30 days after last dose.

¹⁰ New cancer treatments only

| ITT | Intent-to-treat |
| IVRS | Interactive voice response system |
| IWRS | Interactive web response system |
| LDH | Lactate dehydrogenase |
| MedDRA | Medical Dictionary for Regulatory Activities |
| OS | Overall survival |
| PHR | Proportional hazards regression |
| PT | Preferred Term |
| RFS | Recurrence-Free Survival |
| SAE(s) | Serious adverse event(s) |
| SAP | Statistical Analysis Plan |
| SOC | System Organ Class |
| TEAE(s) | Treatment-emergent adverse event(s) |
| WHO | World Health Organization |

1.0 INTRODUCTION

This statistical analysis plan covers the detailed procedures for performing statistical analyses and producing tables, listings, and figures in the Phase III study described in Polynoma Protocol 103A-301 (Version 10.0, dated August 5, 2016). This analysis plan has been updated after the unblinding of the Part A database. This analysis plan supplements the study protocol.

2.0 STUDY DESIGN

2.1 General Study Design and Plan

This is a multi-arm, multicenter, randomized, double-blind, placebo-controlled study composed of several parts: Part A, an open-label extension of Part A, and Parts B1 and B2

Part A is an evaluation of immunological activity and safety. The open-label extension of Part A is an evaluation of the safety and efficacy of seviprotimut-L in subjects who received placebo in Part A.

Part A is designed to evaluate the safety and biological activity of 40 µg and 100 µg of seviprotimut-L compared to placebo, and to select a dose for Part B based on immunological biomarker response. Due to variability in the vials of vaccine from different manufacturing runs, the actual doses administered could have ranged from 24 to 56 µg in the 40 µg arm and from 72 to 160 µg in the 100 µg arm. This evaluation will take place after the first 99 randomized subjects have reached Week 10 (5 doses of study treatment received). Enrollment into Part A will continue until completion of the Part A analysis. Missing or mishandled samples may result in not all dosed subjects being evaluable for the formal Part A analysis. Part A subjects are not included in the Part B primary efficacy evaluations.

The open-label extension (Protocol 103A-301OL) is available exclusively to subjects in Part A of Protocol 103A-301 who were randomized to receive placebo.

[figure not shown]
Part B implements the clinical efficacy evaluation. Originally Part B was a single trial. This amendment splits the study into Parts B1 and B2. Part B1 is double-blind with subjects randomized in a 2:1 ratio to seviprotimut-L or placebo, respectively. Part B2 is double-blind with subjects randomized in a 1:1 ratio to seviprotimut-L or placebo, respectively. Subjects in Parts B1 and B2 will be treated for 24 months with either the dose selected for Parts B (40 µg) or placebo and followed for recurrence and survival. Due to variability among manufacturing runs of the vials of vaccine, the nominal dose of 40 µg may actually be administered as 24 to 56 µg. Individual subjects will not be unblinded at recurrence or the end of treatment in either Part B1 or B2 except to allow the subject to pursue other treatments options.

Part B1 is a clinical efficacy evaluation (with RFS as the sole primary endpoint) as well as a full safety evaluation compared with placebo in order to assess justification for Part B2. Part B1 has a relaxed type I error probability. A total of 325 subjects will be enrolled into Part B1. Clinical outcome data from Part A and the open-label extension of Part A are not used in the evaluation of clinical outcomes from Parts B1 or B2.

Part B2 is a clinical efficacy evaluation (RFS and Survival) as well as a full safety evaluation compared with placebo and will serve as the pivotal trial. 800 subjects will be randomized into Part B2. Part B2 is designed to standalone and will not use data from Parts A or B1.

Figure 1. Study Flow Diagram

Part A Overview

Overall Study Design:

Doses at W0, W2, W4, W6, W8, M3, M4, M5, M6, then every 3 months through M24**.

[figure not shown]
Key Assessments:

- Safety
- Immunological Response (measured at Week 10)
- Collection of blood samples over 3 years for later analysis of biological activity

* Enrollment in Part A is expected to exceed 99 subjects, as enrollment will continue until the 99th subject completes Week 10.

**At the completion of Part A analysis, subjects receiving 40 or 100 µg POL-103A will continue with the dose to which they have been initially randomized to (i.e., Part A subjects will not cross into Part B). Part A placebo subjects will be removed from the study and may be given the option of enrolling in open-label extension protocol 103A-301OL (Part B dose).

Part B Overview

2.2 Randomization and Method of Treatment Assignment

Subjects in Part A will be randomized in a 1:1:1 ratio to placebo or one of two doses of seviprotimut-L. Subjects in Part B1 will be randomized in a 2:1 ratio to the dose selected from Part A or placebo. Subjects in Part B2 will be randomized in a 1:1 ratio to the dose selected from Part A or placebo. Randomization will take place across all study sites using a centralized Interactive Voice/Web Response System (IVRS/IWRS).

At the time of randomization, the IVRS/IWRS will be used to stratify the population according to disease state (IIB/IIC vs. IIIA vs. IIIB/IIIC) to ensure balanced distribution between the seviprotimut-L and placebo arms. Randomization was based on permuted block design with a fixed block size that is a trial secret.

The investigator and subject will be blinded as to treatment assignment; the placebo injections will appear identical to the seviprotimut-L injections.

2.3 Study Procedures Part A

| Procedure | Screening | Dosing Period | | | | | | | | | | | | | | | Pre-Recurrence | | Post-Recurrence | End of Study ¹ |
|------------------------------------|----------------|------------------|-----|-----|-----|-----|------|-----|-----|-----|-----|-----|------|------|------|------|----------------|-----------------|-----------------|---------------------------|
| | | First Visit (W0) | W 2 | W 4 | W 6 | W 8 | W 10 | M 3 | M 4 | M 5 | M 6 | M 9 | M 12 | M 15 | M 18 | M 21 | M 24 | Q 3 Mos | Q 6 Mos | Q 6 Mos |
| Baseline Documentation | | | | | | | | | | | | | | | | | | | | |
| Informed Consent | X | | | | | | | | | | | | | | | | | | | |
| Randomization | | X | | | | | | | | | | | | | | | | | | |
| Medical History | X | X | | | | | | | | | | | | | | | | | | |
| Physical Exam | X | X | | | | | | X | | | X | X | X | X | X | X | X | | X | X |
| Pathology Review | X | | | | | | | | | | | | | | | | | | | |
| BRAF mutation status ² | X | | | | | | | | | | | | | | | | | | | |
| Laboratory Studies | | | | | | | | | | | | | | | | | | | | |
| Immune Response | | X | | | | | X | | | X | | X | | X | | X | | X ³ | | X ⁴ |
| LDH | X | X | | | | | | X | | | X | X | X | X | X | X | X | X | X | X ⁵ |
| CBC and serum chemistry | X | X | X | X | X | X | X | X | | X | | X | | X | | X | | X | | X |
| Urinalysis | X | X | X | X | X | X | X | X | | X | | X | | X | | X | | X | | X |
| Pregnancy test | X | | | | | | | | | | | | | | | | | | | X |
| Serum FSH/estradiol | X | | | | | | | | | | | | | | | | | | | |
| ECG | X | | | | | | | X | | | | X | | | | | | | | X |
| HIV test | X | | | | | | | | | | | | | | | | | | | |
| ANA/ESR | X | | | | | | | | | X | | X | | X | | X | | X | | |
| Tumor Assessments | | | | | | | | | | | | | | | | | | | | |
| Recurrence Assessment ⁶ | X ⁷ | | | | | | | | | X | | X | | X | | X | | X | | |
| Dosing | | | | | | | | | | | | | | | | | | | | |
| Seviprotilum-L or placebo | | X | X | X | X | X | | X | X | X | X | X | X | X | X | X | X | | | |
| Other Clinical Assessments | | | | | | | | | | | | | | | | | | | | |
| Survival Follow-up Contact | | | | | | | | | | | | | | | | | | | X | |
| Autoimmune Phenomena ⁸ | X | | | | | | | | | X | | X | | X | | X | | | | |
| Adverse Events | | X | X | X | X | X | X | X | X | X | X | X | X | X | X | X | X | X ⁹ | | |
| Concomitant Medications | X | X | X | X | X | X | X | X | X | X | X | X | X | X | X | X | X | X ¹⁰ | X | |

¹ At time of recurrence or study completion for subjects without recurrence

² BRAF tumor mutation V600E status must be either known at Screening or a tumor tissue (fresh or archived sample) must be available for testing during the Study.

³ Blood samples for immune monitoring at visits at Months 30 and 36 only.

⁴ If within 36 months of randomization into study

⁵ For subjects who have not had recurrent disease

⁶ See Section 9.3.1 of the Protocol for details

⁷ To be performed if the protocol-specified assessments have not been performed after the surgical resection, or the data are not available to the Sponsor

⁸ Include eye exam (by an ophthalmologist) and skin exam for vitiligo and rashes thereafter.

⁹ Adverse events collected through 30 days after last dose.

¹⁰ New cancer treatments only

